## PROTOCOL AMENDMENTS

Amendments below are listed beginning with the most recent amendment.

---

### **Amendment 2** (This document)

This amendment is considered to be nonsubstantial based on the criteria set forth in Article 10(a) of Directive 2001/20/EC of the European Parliament and the Council of the European Union, in that it does not significantly impact the safety or physical/mental integrity of subjects, nor the scientific value of the study.

**The overall reason for the amendment:** The overall reason for this amendment was to provide more clarity when the clinician questionnaire needs to be completed. Furthermore, it was clarified that the entry visit needs to take place within 3 months after randomization in Study 64041575RSV2004 and that the study site visits need to be scheduled 3, 6, 12, 18, and 24 months after entry visit in Study 64041575RSV2002.

---

The table below gives an overview of the rationale for each change and all applicable sections.

---

**Rationale:** It was clarified that the clinician questionnaire needs to be completed during the scheduled study site visits (entry visit and 3, 6, 12, 18, and 24 months after entry visit) and during monthly telephone calls with the parent/caregiver between study site visits as indicated in the Time and Events Schedule. Instructions in the paper questionnaire and footnote “b” of the Time and Events Schedule were updated accordingly. Furthermore, it was clarified that the entry visit needs to take place within 3 months after randomization in Study 64041575RSV2004 and that the study site visits need to be scheduled 3, 6, 12, 18, and 24 months after entry visit in Study 64041575RSV2002.

---

### SYNOPSIS

#### Time and Events Schedule

#### 9.1.2 Entry Visit

#### 9.1.3 Study Period

#### Attachment 2

---

**Rationale:** A window of  $\pm 7$  days from the entry visit is allowed for the other scheduled study site visits.

---

#### Time and Events Schedule

---

**Rationale:** The protocol is aligned with the sponsor’s latest available protocol template and minor corrections were made, including but not limited to:

- The classification of this study as an observational or interventional study depends on local regulation. Therefore the word “observational” was removed from the protocol.
- 

Throughout the protocol

---

### **Amendment 1** (26 June 2017)

This amendment is considered to be nonsubstantial based on the criteria set forth in Article 10(a) of Directive 2001/20/EC of the European Parliament and the Council of the European Union, in that it does not significantly impact the safety or physical/mental integrity of subjects, nor the scientific value of the study.

**The overall reason for the amendment:** The overall reason for this amendment was to clarify that participation in this long-term follow-up study is optional for study sites, update the study number for which this study will be the long-term follow-up study (64014575RSV2004), update the introduction and background information to be in line with Study 64014575RSV2004, update the age of subjects participating in Study 64014575RSV2004, and update the planned number of subjects to be enrolled in Study 64041575RSV2004. In addition, minor editorial changes, clarifications, and corrections were made.

---

---

The table below gives an overview of the rationale for each change and all applicable sections.

---

**Rationale:** Language was added to clarify that participation in this long-term follow-up study is optional for study sites.

---

SYNOPSIS

3.1 Overview of Study Design

---

**Rationale:** The study number for Study 64041575RSV2001 was changed to 64041575RSV2004. Due to significant changes in the study design a new protocol number was created for this study. Additional changes were also made to align Study 64041575RSV2002 with Study 64041575RSV2004 and included the following:

- The introduction and background information was updated to be in line with Study 64041575RSV2004 and the updated version of the Investigator's Brochure (Edition 7).
  - The age of infants and children participating in Study 64041575RSV2004 was updated from 1 to 36 months to  $\geq 28$  days to  $\leq 36$  months, according to the 64041575RSV2004 protocol.
  - The planned number of subjects to be enrolled in Study 64041575RSV2004 was updated according to the 64041575RSV2004 protocol.
- 

Throughout the protocol

SYNOPSIS

1 INTRODUCTION

1.1 Background

11.2 Sample Size Determination

---

**Rationale:** Minor editorial changes, clarifications, and corrections were made, including but not limited to:

- The generic name of the investigational product, lumicitabine, was added. The compound numbers of the investigational product and its metabolites were also updated to the current compound numbers.
  - A definition was added to explain that "previous treatment group" refers to the actual treatment (lumicitabine or placebo) administered in Study 64041575RSV2004.
  - Clarification was made that wheezing and medication parent/caregiver cards will be completed on a daily basis and that these cards will aid the study site personnel to complete the clinical questionnaire when they interview the parent/caregiver. The wheezing and medication parent/caregiver cards were added as attachments to the protocol.
  - A paper questionnaire instead of an electronic device will be used for completion of the clinical questionnaire.
- 

Throughout the protocol

SYNOPSIS

3.1 Overview of Study Design

8 Medications

9.1 Study Procedures

11.3.1 Primary Analysis

15 STUDY-SPECIFIC MATERIALS

---

## SYNOPSIS

### A Long-term Follow-up of Study 64041575RSV2004 to Evaluate the Impact of Lumicitabine (JNJ-64041575) on the Incidence of Asthma and/or Wheezing in Infants and Children with a History of Respiratory Syncytial Virus Infection

Lumicitabine (also known as JNJ-64041575 or ALS-008176) is a 3',5'-bisisobutyrate prodrug of the cytidine nucleoside analog JNJ-63549109 (also known as ALS-008112), which is being developed as an orally administered antiviral therapy for the treatment of infants, children, and adults infected with respiratory syncytial virus (RSV) and human metapneumovirus. Once administered, lumicitabine is rapidly and efficiently converted by esterases to JNJ-63549109. Inside cells, JNJ-63549109 is subsequently converted to the JNJ-63549109-5'-triphosphate, JNJ-65409136 (also known as ALS-008136), which, as the active metabolite of the compound, is a potent and selective inhibitor of RSV and human metapneumovirus ribonucleic acid (RNA) polymerase activity via a classic chain termination mechanism. JNJ-64167896 (also known as ALS-008144), the uridine metabolite of JNJ-63549109, is the inactive major metabolite noted in systemic circulation.

#### Investigational Product and its Metabolites

Compound Name/Number	Description
Lumicitabine (JNJ-64041575, ALS-008176)	3',5'-bisisobutyrate prodrug of JNJ-63549109
JNJ-63549109 (ALS-008112)	parent nucleoside, major metabolite of lumicitabine
JNJ-64412309 (ALS-008206)	3'-isobutyrate monoester of JNJ-63549109, minor metabolite
JNJ-64412296 (ALS-008207)	5'-isobutyrate monoester of JNJ-63549109, minor metabolite
JNJ-64167896 (ALS-008144)	uridine metabolite of JNJ-63549109, major metabolite
JNJ-65409136 (ALS-008136)	5'-triphosphate of JNJ-63549109 (NTP), intracellular metabolite, active
JNJ-65409123 (ALS-008137)	5'-monophosphate of JNJ-63549109, intracellular metabolite

Abbreviation: NTP: nucleoside triphosphate.

This long-term follow-up (LTFU) study will evaluate the incidence of the clinical diagnosis of asthma and the frequency of wheezing for at least 2 years in subjects enrolled from Study 64041575RSV2004.

## OBJECTIVES, ENDPOINTS, AND HYPOTHESIS

### Objectives

#### Primary Objectives

The primary objectives are to evaluate in infants and children who have been treated with lumicitabine or placebo in Study 64041575RSV2004 during the follow-up period and within 2 years after the RSV infection:

- The incidence of the clinical diagnosis of asthma.
- The frequency of wheezing.

#### Secondary Objectives

The secondary objectives are to evaluate during the follow-up period in infants and children who have been treated with lumicitabine or placebo in Study 64041575RSV2004:

- The frequency of wheezing over time.
- The frequency of wheezing episodes over time.
- The long-term safety of lumicitabine.

- The frequency and type of respiratory infections.
- Medical resource utilization.

### ***Exploratory Objectives***

The exploratory objectives are to evaluate during the follow-up period in infants and children who have been treated with lumicitabine or placebo in Study 64041575RSV2004:

- The long-term impact of RSV and its treatment with lumicitabine or placebo on how the subject's health affects normal daily activities for subjects, parents/caregivers, and other family members.
- Impact of the type of wheezing/asthma phenotypes on the frequency of wheezing and clinical diagnosis of asthma.

### **Endpoints**

#### ***Primary Endpoints***

The primary endpoints are:

- Clinical diagnosis of asthma within the first 2 years after the RSV infection, as diagnosed by a physician and reported by the parent/caregiver.  
All medical information needed to confirm the diagnosis of asthma needs to be collected by the study site personnel.
- Percentage of wheezing days within the first 2 years after the RSV infection, based on information reported by the parent/caregiver.

#### ***Secondary Endpoints***

The secondary endpoints during the follow-up period are:

- Percentage of wheezing days per month after the RSV infection, based on information reported by the parent/caregiver.
- Number of wheezing episodes after the RSV infection, based on information reported by the parent/caregiver.
- Incidence of reportable adverse events (AEs) and serious adverse events (SAEs) among subjects, based on information reported by the parent/caregiver and judged by the investigator. Reportable AEs include AEs related to respiratory illnesses and AEs considered at least possibly related to lumicitabine or placebo by the investigator.
- Number and type of respiratory infections among subjects, based on information reported by the parent/caregiver.
- Medical resource utilization including the number of medical visits, emergency room visits, and hospitalizations, all for respiratory conditions only, based on information reported by the parent/caregiver.

### ***Exploratory Endpoints***

The exploratory endpoints during the follow-up period are:

- The long-term impact of RSV and its treatment with lumicitabine or placebo on how the subject's health affects the normal daily activities of the subject, the parent/caregiver, and other family members as determined by:
  - The extent to which the subject's daily activities each month were limited by the subject's health.
  - The percentage of days each month that the parent/caregiver missed from work due to the subject's health.
  - The extent to which the parent's/caregiver's productivity while at work was limited by the subject's health.
  - The extent to which the subject's health problems limited the parent's/caregiver's ability to engage in normal daily activities.
  - The extent to which the subject's health problems impacted the parent's/caregiver's health.
  - The inability of the parent/caregiver to care for other family members due to the subject's health.
  - The extent to which the subject's health limited the parent's/caregiver's time spent with other family members.
  - The percentage of days each month that other family members missed from work due to the subject's health problems.
- Frequency of wheezing and clinical diagnosis of asthma by type of wheezing/asthma phenotype.

### **Hypothesis**

No formal hypothesis testing will be performed. The hypothesis to be explored is that treatment of RSV-infected infants and children with lumicitabine will decrease the incidence of subsequent asthma and/or wheezing compared with infants and children treated with placebo.

### **OVERVIEW OF STUDY DESIGN**

This is a global, multicenter, blinded, LTFU study to evaluate the incidence of the clinical diagnosis of asthma and the frequency of wheezing in infants and children (otherwise healthy or with underlying comorbidities for severe RSV) who have completed their treatment course and their last study-related visit in a previous Phase 2 study, 64041575RSV2004, in which they received lumicitabine or placebo for the treatment of RSV infection. Subjects will be followed for at least 2 years following treatment. This study may be extended up to an additional 3 years (ie, total duration up to 5 years after randomization into Study 64041575RSV2004). Participation in this LTFU study is optional for study sites. This LTFU study will be offered to subjects of Study 64041575RSV2004 if their site decides to participate in this LTFU study.

Subjects will be enrolled within 3 months after randomization in Study 64041575RSV2004.

No study drug will be administered in this study. The parent/caregiver of the subject and the investigator will remain blinded to the study treatment (lumicitabine or placebo) administered in Study 64041575RSV2004 until the completion of this LTFU study, including any extension period.

Assessments will be performed at the study site at enrollment in this study and at 3, 6, 12, 18, and 24 months after entry visit in Study 64041575RSV2002. The last visit of Study 64041575RSV2004 (ie,

Day 28) may be combined with the entry visit of this LTFU study. The same assessments will be performed during monthly phone calls with the parent/caregiver between the study site visits.

An unblinded interim analysis will be performed when all subjects from the first season in Study 64041575RSV2004 who are enrolled in this LTFU study complete the 18 month follow-up assessment of this LTFU study. This interim analysis will serve to evaluate the need for an extension of the follow-up period.

### **SUBJECT POPULATION**

Male or female infants and children who were previously randomized in Study 64041575RSV2004 for the treatment of RSV infection, who completed the planned course of the study drug and the last study-related visit in Study 64041575RSV2004, and whose legally acceptable representative has signed the informed consent form are eligible for participation in this LTFU study.

### **DOSAGE AND ADMINISTRATION**

No study drug will be administered in this study.

### **CLINICAL EVALUATIONS**

The study includes the following clinical evaluations:

- Collection of information on the clinical diagnosis of asthma to determine the incidence of asthma.
- Collection of presence of wheezing on a daily basis to determine the frequency of wheezing and wheezing episodes.
- Collection of medical history and family history to identify risk factors for wheezing/asthma at baseline.
- Collection of data to determine the frequency and type of respiratory infections.
- Collection of data on medications used for the treatment of respiratory infections and illnesses (eg, bronchodilators).
- Collection of data from lung function tests and allergy tests (immunoglobulin E and skin test), if available, as supporting documentation of the diagnosis of asthma, wheezing, and atopy.

### **MEDICAL RESOURCE USAGE AND HEALTH ECONOMICS**

Medical resource usage (including medical visits, emergency room visits, and hospitalizations, all for respiratory conditions) and the impact of the subject's health status on normal daily activities for subjects, parents/caregivers, and other family members will be collected throughout the course of the study.

### **SAFETY EVALUATIONS**

The study includes the following evaluations of safety and tolerability:

- Respiratory illness AEs (including subsequent RSV infections).
- AEs considered at least possibly related to lumicitabine or placebo.
- SAEs.

### **STATISTICAL METHODS**

No formal power calculation has been performed, as this is an LTFU study in which infants and children from the previous Phase 2 study of lumicitabine (Study 64041575RSV2004) may be enrolled. The planned number of subjects enrolled in Study 64041575RSV2004 is up to 120 subjects on lumicitabine

and up to 60 subjects on placebo. It is expected that approximately 35% of those subjects will participate in this LTFU study.

The final analysis will be done when all the subjects have completed the last planned assessment of the follow-up period or discontinued earlier.

The primary endpoints in this study are the clinical diagnosis of asthma and the percentage of wheezing days in a subject within the first 2 years after the RSV infection, as reported by the parent/caregiver.

No statistical testing will be done.

Estimates of the incidence of asthma will be presented together with the 95% (2-sided) confidence interval by previous treatment group. The previous treatment group is defined as the actual treatment (lumicitabine or placebo) of Study 64041575RSV2004. As a sensitivity analysis, the incidence of asthma will be presented for the subgroup of subjects for whom at least 12 months of follow-up data are available.

The percentage of days with wheezing within the first 2 years after the RSV infection will be calculated per subject. Descriptive statistics, including 95% confidence intervals, will be presented by previous treatment group.

For the secondary endpoint, descriptive statistics and frequency tabulations will be used to present the percentage of wheezing days per month, the mean number of wheezing episodes, and the number and type of respiratory infections by previous treatment group.

Long-term safety of lumicitabine, medical resource utilization, and impact of the subject's health status on normal daily activities for subjects, parents/caregivers, and other family members will be evaluated using frequency tabulations and listings by previous treatment group.

**TIME AND EVENTS SCHEDULE**

Study Period	Entry Visit a,b	Assessment Period b				
	Months	0	3 (±7 days)	6 (±7 days)	12 (±7 days)	18 (±7 days)
Screening/Administrative						
Informed consent	X					
Eligibility criteria	X					
Baseline demographics c	X					
Medical and family history c,d	X					
Wheezing and medication parent/caregiver card distribution and verification e,f	X	X	X	X	X	X
Clinical Evaluations						
Clinician questionnaire g	X	X	X	X	X	X
	Monthly telephone calls between study site visits h					
Collection of data from lung function tests and allergy tests (immunoglobulin E and skin tests) i			X			
Medical resource utilization j			X			
Medication l			X			
Safety Evaluations						
Serious/reportable adverse events k			X			

- a. The entry visit needs to take place within 3 months after randomization in Study 64041575RSV2004. The last visit of Study 64041575RSV2004 (ie, Day 28) may be used as the entry visit for this study.
- b. Assessments will be performed during study site visits (entry visit and 3, 6, 12, 18, and 24 months after entry visit in Study64041575RSV2002) and during monthly telephone calls with the parent/caregiver between study site visits.
- c. Baseline demographics and medical/family history from the previous Phase 2 Study 64041575RSV2004 will be captured in the long-term follow-up electronic case report form (eCRF).
- d. Medical and family history to identify risk factors for wheezing/asthma at baseline, including prenatal smoking by the subject's mother, subject's exposure to tobacco smoke, wheezing associated with symptoms of acute respiratory infections, whether the subject has siblings or attends kindergarten/day care, and personal and/or family history of atopy/allergy will be recorded in the eCRF.
- e. Parents/caregivers will be provided with a wheezing parent/caregiver card to be completed daily. The information recorded on the wheezing parent/caregiver card will aid the site responsible person to complete the clinical questionnaire when interviewing the subject's parent/caregiver. Parents/caregivers will be required to return the completed parent/caregiver cards to the study sites every 3 months (eg, in person or by mail/email/fax when no study site visit is scheduled).
- f. Medication use will be monitored throughout the study from signing of the informed consent form until the last study-related activity. Parents/caregivers will be required to bring all medications to the study site visit. Additionally, parents/caregivers will be required to document on a daily basis use of all medications on a medication parent/caregiver card, which will serve as a reminder card to be used during the study site visits and during the monthly phone calls between the study site visits for recording the medication used for respiratory infections and illnesses in the eCRF by the study site personnel. Parents/caregivers will be required to return the completed parent/caregiver cards to the study sites every 3 months (eg, in person or by mail/email/fax when no study site visit is scheduled).
- g. Collection of data on wheezing, asthma, eczema, allergic rhinitis, and impact of the subject's health status on normal daily activities for subjects, parents/caregivers, and other family members using a standardized questionnaire. The questionnaire should preferably be completed by the same study site responsible person, by

interviewing the subject's parent/caregiver. Parents/caregivers will complete the wheezing and medication parent/caregiver cards on a daily basis, which will aid the study site responsible person in completing the questionnaire during the interview. Parents/caregivers will be required to return the completed parent/caregiver cards to the study sites every 3 months (eg, in person or by mail/email/fax when no study site visit is scheduled).

- h. Once per calendar month ( $\pm 7$  days) from the entry visit.
- i. Data from lung function tests and allergy tests (immunoglobulin E and skin test), if available, will be collected as supporting documentation of the diagnosis of asthma, wheezing, and atopy as reported by the parent/caregiver.
- j. Medical resource utilization will be monitored throughout the study from signing of the informed consent form until the last study-related activity and will include medical visits, emergency room visits, and hospitalizations, all for respiratory conditions only and will be recorded in the eCRF. Visits with each type of health care provider (eg, general practitioner, pediatrician, physician assistant, nurse practitioner, pulmonologist, allergist, or other) will be specified in the eCRF.
- k. All reportable adverse events and serious adverse events will be monitored throughout the study from signing of the informed consent form until the last study-related activity and recorded in the eCRF.

---

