## 10.2. Withdrawal From the Study

A subject will be automatically withdrawn from the study for any of the following reasons:

- Lost to follow-up.
- Withdrawal of consent.
- Death.

If a subject is lost to follow-up, every reasonable effort must be made by the study site personnel to contact the parent/caregiver and determine the reason for withdrawal. The measures taken to follow up must be documented.

When a subject is withdrawn by his/her parent(s)/caregiver(s) before completing the study, the reason for withdrawal is to be documented in the eCRF and in the source document.

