2. GENERAL ANALYSIS DEFINITIONS

2.1. Visit Windows and Phase definition

As this is a LTFU of Study 64041575RSV2004, only 1 analysis phase will be defined (see [Table 1](#)). The reference is the date of informed consent in study 64041575RSV2002.

Table 1: Trial Phase

Trial Phase	Trial Phase (Numeric Version)	Start Date	End Date
Long Term Follow Up	1	00:00 of the date of signing the informed consent	Trial termination date (date of last contact) with timestamp 23:59

For assigning assessments, the visit schedule as reported in the database will be used.

If a subject has a missing visit, the data will be set to missing and will not be imputed. Information of an unscheduled visit will be merged with the scheduled visit, meaning that any information will be added to scheduled visit data.

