5. EFFICACY

5.1. Primary Efficacy Endpoint(s)

5.1.1. Definition

The primary endpoints are:

1. Clinical diagnosis of asthma within the first 2 years after the RSV infection, as diagnosed by a physician and reported by the parent/caregiver. This will be derived based on the completed study questionnaires at each visit/telephone call until the final visit. It is either “Yes” or “No”.
2. The percentage of wheezing days in a subject within the first 2 years after the RSV infection will be calculated as:

$$\text{Percentage of wheezing days} = \left(\frac{\text{number of wheezing days}}{\text{day of study completion} - \text{day of informed consent} + 1} \right) * 100$$

The percentage will be rounded to the nearest integer. Number of wheezing days is the sum of all days that were reported in the Monthly visit reports. The day of informed consent is the informed consent of the RSV2002 study.

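### Nothing requires a final questionnaire or card return when a child is withdrawn, so events since the last monthly contact may be missing from both primary endpoints

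*Protocol*

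**What the plan says.** Protocol, Time and Events Schedule, footnote b: "Assessments will be performed during study site visits (entry visit and 3, 6, 12, 18, and 24 months after entry visit in Study64041575RSV2002", with telephone calls between those visits. Footnote h sets the calls at "Once per calendar month", within 7 days either way. No column or footnote covers early withdrawal.

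Protocol 10.2 names three reasons for withdrawal: loss to follow-up, withdrawn consent and death. For a child lost to follow-up, "every reasonable effort must be made by the study site personnel to contact the parent/caregiver and determine the reason for withdrawal". For a child withdrawn by the parent, "the reason for withdrawal is to be documented in the eCRF and in the source document". Neither sentence asks for a last questionnaire or for the outstanding cards.

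SAP 5.1.1 says of the asthma endpoint: "This will be derived based on the completed study questionnaires at each visit/telephone call until the final visit". Of its values it says "It is either “Yes” or “No", with no missing category and no minimum follow-up. Wheezing days are summed from the monthly reports. They are divided by the days from informed consent to the day of study completion. Protocol 10.1 ties completion to the Month 24 assessments, so a leaver has no such day. The nearest end date in the SAP is in Table 1 of section 2.1: "Trial termination date (date of last contact) with timestamp 23:59". The same section says: "If a subject has a missing visit, the data will be set to missing and will not be imputed". It does not link that rule to the asthma derivation.

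**The concern.** Leavers are foreseen: Protocol 11.3 includes children who discontinue early in the final analysis, and SAP 4.2 tabulates them. For such a child, the days between the last questionnaire and departure fall outside anything the plan obliges a site to collect. A diagnosis in those days has no required route to a Yes. The same days may also lengthen the wheezing denominator without adding to the numerator, which biases that child's percentage downward.

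The plan is more careful elsewhere. Protocol 12.2.2 requires unresolved serious adverse events to be followed after discontinuation. SAP Table 2 shortens the adverse event divisor when a child took part for less than 24 months. The primary endpoints have no equivalent. The protocol's sensitivity analysis in children with at least 12 months of data (11.3.1) has no counterpart in the SAP, which defines no subsets (2.4).

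**Working it through.** The documents state no dropout rate, asthma rate or power figure, so the plan has no figure of its own to reproduce.

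Inputs from the documents:
- monthly contacts, 7 days either way (schedule, footnote h)
- a 2-year endpoint window, taken as 730 days
- 7 children enrolled (SAP 2.4), with the split by arm not given

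Assumptions, not in the documents:
- a 24-month asthma risk p of 5% to 30%, with constant hazard
- a true wheezing frequency of 10% of days, the same in covered and uncovered time
- arm sizes and the timing of withdrawal

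**1. Length of the gap.** One month is up to 31 days. With both windows used, two on-time contacts are at most 31 + 7 + 7 = 45 days apart. As shares of the window, 31/730 = 4.2% and 45/730 = 6.2%. The gap is longer if calls were missed before the child left.

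**2. Chance of a diagnosis in the gap.** For a child undiagnosed at the last questionnaire, the hazard is λ = −ln(1 − p)/730 and the chance is 1 − exp(−λg) for a gap of g days.
- p = 5%: 0.22% for g = 31 and 0.32% for g = 45
- p = 30%: 1.50% for g = 31 and 2.17% for g = 45

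The range is therefore about 0.2% to 2.2% per leaver. If all 7 children left with a 45-day gap, the expected number of missed diagnoses would be 7 × 0.32% = 0.02 to 7 × 2.17% = 0.15.

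**3. Wheezing percentage.** If the end date is a withdrawal contact without a questionnaire, the reported value is 10% × covered days/(covered days + gap).
- 182 covered days: 18.2/213 = 8.5% (31-day gap) or 18.2/227 = 8.0% (45-day gap)
- 365 covered days: 36.5/396 = 9.2% (31-day gap) or 36.5/410 = 8.9% (45-day gap)

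The SAP rounds to whole percentages, so the first pair would print as 9% and 8%, and both values of the second pair as 9%. If the last contact was itself a questionnaire, as is typical for loss to follow-up, the gap is zero and so is the dilution.

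**4. Effect of one reclassified child.** Overall, the Wilson 95% interval is 0% to 35.4% for 0/7 and 2.6% to 51.3% for 1/7. In an assumed arm of 3, it is 0% to 56.1% for 0/3 and 6.1% to 79.2% for 1/3. In assumed arms of 2 to 5, one child moves the proportion by 1/2 = 50 to 1/5 = 20 percentage points. These shifts are conditional on the event in step 2, which is unlikely.

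**5. Time after withdrawal.** For a child who leaves at Month 12, the chance, counted from the start of the 24 months, that the diagnosis falls in the second year is √(1 − p) − (1 − p). This is 2.5% at p = 5% and 13.7% at p = 30%. It exceeds the gap in step 2, and a withdrawal questionnaire alone does not recover it.

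**The case against.** A reader might infer that the last interval is never collected. The documents do not go that far. Reportable adverse events, medication and respiratory medical visits are followed to the last study activity. Adverse event reporting may include a later safety contact (Protocol 12.2.1). Cards may be sent by mail, email or fax. SAP 2.1 merges unscheduled-visit information into the scheduled visit, so a questionnaire taken voluntarily at withdrawal could be used. This stands as far as it goes. However, adverse event and resource-use records do not feed the primary derivations, and none of these routes is required at withdrawal.

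A reader might also take it as settled that a leaver's late diagnosis is scored No. That is an inference from a two-valued endpoint built on completed questionnaires. No text says how a child with partial follow-up is classified.

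Nor do the documents support the idea that a new asthma diagnosis drives children out of the study. Care follows local practice, medication is unrestricted, and pulmonologist and allergist visits are expected and recorded. Departure linked to the outcome is possible, but nothing in the plan points to it.

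The remaining objections concern yield, and they stand. A withdrawal contact helps only families who can be reached and are willing. The probability in step 2 is low, the analysis is descriptive, only 7 children enrolled, and SAP section 3 records that the project was stopped.

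**Conclusion.** The gap is real but limited. No provision requires the questionnaire or the outstanding cards at withdrawal, so up to about 45 days per leaver may be missing from both primary endpoints if contacts were on time. The chance of losing a diagnosis this way is about 0.2% to 2.2% per leaver, under the assumed risks and constant hazard. The wheezing dilution, 10% read as about 8.0% to 8.5% after 182 covered days, arises only if a contact without a questionnaire sets the end date. The SAP leaves that date open for leavers. If nobody leaves, there is no effect.

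The larger exposure is in step 5: a child with partial follow-up can, by the same inference, stand as No for the full two years. This is a cheap improvement worth making, not a flaw that undermines the study.

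**What to change.** **Protocol, schedule and section 10.2.** Add an early-withdrawal contact. When a child is withdrawn other than by death, and the parent can be reached and agrees:
- complete the Attachment 2 questionnaire, by phone if needed, for the time since the last contact
- collect outstanding cards
- record reportable adverse events
- ask for agreement to one question on asthma diagnosis at the planned Month 24 date

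The form already asks about the time since the last contact and is already used by phone. The Month 24 question is the only element that addresses time after withdrawal.

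**SAP 5.1.1.** End the wheezing denominator at the last day covered by a questionnaire. For children without a recorded diagnosis and without 24 months of questionnaires, report asthma status as incomplete follow-up, not as No for the full two years.

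**Cost.** The protocol part needs an amendment with ethics committee approval (Protocol 17.1), a call per leaver and the later question where agreed. Some parents will decline. With 7 children and the project stopped, it can recover little now. The SAP part needs no new data and can still be applied.
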